# 4.1.3 Exploratory

- 4.1.3.1 To assess the potential role, if any, of TDM of isavuconazole levels in the prophylactic setting in patients with newly diagnosed AML/MDS receiving cytotoxic chemotherapy or other therapies.
- 4.1.3.2 To determine the *in vitro* susceptibility of agents causing "breakthrough" IFIs to antifungal agents.

# 4.2 ENDPOINTS

# 4.2.1 Primary

4.2.1.1 Incidence of proven or probable IFI (by EORTC/MSG criteria) during the first 100 days from initiation of isavuconazole prophylaxis.

# 4.2.2 Secondary

- 4.2.2.1 Incidence of IA within 100 days of isavuconazole prophylaxis initiation.
- 4.2.2.2 Incidence of other IFIs within 100 days of isavuconazole prophylaxis initiation.
- 4.2.2.3 Rates of treatment success vs. failure (defined above).
- 4.2.2.4 Overall survival.
- 4.2.2.5 Survival without proven or probable IFI.
- 4.2.2.6 Time to death from any cause.
- 4.2.2.7 Time to death related to IFI.
- 4.2.2.8 Time to diagnosis of proven or probable IFI.
- 4.2.2.9 Time to first use of empiric antifungal therapy.
- 4.2.2.10 AEs throughout the duration of isavuconazole prophylaxis until 30 days after the last dose of study drug.

# 4.2.3 Exploratory

- 4.2.3.1 Plasma isavuconazole (trough) levels on day 8 and day 15 using a validated assay.
- 4.2.3.2 Antimicrobial susceptibility testing of fungal isolates from proven "breakthrough" IFIs.

# **5 ELIGIBILITY CRITERIA**

# 5.1 INCLUSION CRITERIA (all criteria must be met)

- 5.1.1 Patients with either newly diagnosed AML or MDS who have either begun (within 4 days of starting study drug) or are planned to begin specific treatment for their AML/MDS. Hydroxyurea and cytarabine used for cytoreduction while awaiting initiation of definitive therapy are not considered "specific"treatment. Patients who are participating in other therapeutic clinical trials for their AML/MDS may participate in this trial.
- 5.1.2 Patients must have or be anticipated to have neutropenia (absolute neutrophil count (ANC) <0.5 x  $10^{9}/L$ ) for  $\geq$ 7 days as a result of treatment of their AML/MDS.
- 5.1.3 Age  $\geq 18$  years.
- 5.1.4 Eastern Cooperative Oncology Group (ECOG) performance status 0, 1 or 2.
- 5.1.5 Patients must have reasonable liver function, i.e., total bilirubin  $\leq 3 \times ULN \text{ AND AST/ALT} \leq 5 \times ULN$ .
- 5.1.6 Patients must be able to take oral medications, although a brief period of IV therapy (<4 days) is permitted at trial entry.
- 5.1.7 Patients must be willing and able to provide written informed consent for the trial.
- 5.1.8 Women of childbearing potential (WOCBP) must practice 2 effective methods of birth control during the course of the study. Male patients who are partners of WOCBP should also practice an effective method of contraception. Effective methods of birth control include diaphragm or condoms with spermicidal foam or jelly, birth control pills (BCPs), injections or patches, intra-uterine devices (IUDs) and surgical sterilization.
- Postmenopausal women must be amenorrheic for  $\geq 12$  months to be considered of non-childbearing potential.

- Women and men must continue birth control for the duration of the trial and ≥3 months after the last dose of study drug.
- All WOCBP MUST have a negative pregnancy test prior to first receiving study medication.

# **5.2 EXCLUSION CRITERIA**

- 5.2.1 Proven, probable or possible IFI (by EORTC/MSG criteria, see sections 9.1 and 9.2) within the previous 30 days.
- 5.2.2 Use of any systemic antifungal therapy for >72 hours during the week prior to study drug initiation.
- 5.2.3 History of hypersensitivity or idiosyncratic reactions to azoles.
- 5.2.4 Patients with familial short QT syndrome or with QTc interval  $\leq$ 300 ms.
- 5.2.5 Patients on strong CYP3A4 inducers or inhibitors that cannot be discontinued.
- 5.2.6 Women who are pregnant or nursing, or intend to be/do so during the course of the study.
- 5.2.7 Patients with severe hepatic impairment (Child-Pugh class C).
- 5.2.8 Patients with known or suspected Gilbert's syndrome at the time of study enrollment.
- 5.2.9 Patients with known gastrointestinal conditions that could potentially interfere with absorption of orally administered medications.
- 5.2.10 Any condition that, in the opinion of the investigator, may interfere with the objectives of the study, e.g., any condition requiring the use of prohibited drugs or unstable medical conditions other than AML/MDS, such as a cardiac or neurologic disorder expected to be unstable or progressive during the course of the study (e.g., seizures or demyelinating syndromes, acute myocardial infarction within 3 months of study entry, myocardial ischemia or unstable congestive heart failure, unstable arrhythmias).

# 6 TREATMENT PLAN

#### 6.1 General

All patients should be registered with the Data Management Office PDMS/CORE system.

Isavuconazonium sulfate will be administered orally in this study. However, IV administration for <4 days will be permitted if required at study entry. During the course of the study, if required (e.g., due to mucositis), switching between the IV and oral formulations of isavuconazonium sulfate is acceptable without dose changes or the need for any loading doses as bioequivalence has been demonstrated. However, every effort should be made to minimize the duration of IV administration.

Dosing will be identical for oral and IV administration of isavuconazonium sulfate. Isavuconazonium sulfate will be administered at a dose of 372 mg (i.e., 2 capsules, or 200 mg of isavuconazole) orally every 8 hours for 6 doses (48 hours), and 372 mg (i.e., 2 capsules, or 200 mg of isavuconazole) orally once daily thereafter. Maintenance doses should be started 12 to 24 hours after the last loading dose.

If IV administration is required at therapy initiation, 372 mg (1 reconstituted vial, or 200 mg of isavuconazole) will be administered IV every 8 hours for 6 doses, followed by 372 mg (1 reconstituted vial, or 200 mg of isavuconazole) IV once daily. Maintenance doses should be started 12 to 24 hours after the last loading dose.

If a switch from oral to IV therapy is needed at a later time point, 1 reconstituted vial IV will be substituted for 2 capsules orally once daily. Treatment should be switched back to the oral route as soon as the patient is able to take oral medications.

Capsules should be swallowed whole. They should not be chewed, crushed, dissolved, or opened. Isavuconazonium sulfate can be taken without regard to food.

#### • Reconstitution Instructions for the Injection Formulation

Aseptic technique must be strictly observed in all handling. Isavuconazonium sulfate is water soluble, preservative-free, sterile, and nonpyrogenic.

- Reconstitute one vial of isavuconazonium sulfate by adding 5 mL water for injection, USP to the vial.
- Gently shake to dissolve the powder completely.
- Visually inspect the reconstituted solution for particulate matter and discoloration. Reconstituted isavuconazonium sulfate should be clear and free of visible particulate.
- The reconstituted solution may be stored below 25°C for maximum 1 hour prior to preparation of the patient infusion solution.

#### • Dilution and Preparation Instructions for the Injection Formulation

- Remove 5 mL of the reconstituted solution from the vial and add it to an infusion bag containing 250 mL (approximately 1.5 mg isavuconazonium sulfate per mL) of compatible diluent. The diluted solution may show visible translucent to white particulates of isavuconazole (which will be removed by in-line filtration).
- Use gentle mixing or roll bag to minimize the formation of particulates. Avoid unnecessary vibration or vigorous shaking of the solution. Do not use a pneumatic transport system.
- Apply in-line filter with a microporous membrane pore size of 0.2 to 1.2 micron and in-line filter reminder sticker to the infusion bag.
- Infuse over a minimum of 1 hour to minimize the risk of infusion-related reactions. Do not administer as an IV bolus. Do not infuse isavuconazonium sulfate with other medications.
- The intravenous administration should be completed within 6 hours of dilution at room temperature. If this is not possible, immediately refrigerate (2° to 8°C / 36° to 46°F) the infusion solution after dilution and complete the infusion within 24 hours. Do not freeze the infusion solution.

#### • Compatibility for the Injection Formulation

Isavuconazonium sulfate for injection should only be administered with the following diluents:

- 0.9% sodium chloride injection, USP
- 5% dextrose injection, USP

# 6.2 Duration of prophylaxis

Study drug treatment will be administered daily continuously until, whichever occurs first:

- recovery from neutropenia (ANC  $\geq 0.5 \times 10^9/L$ ) and attainment of complete remission (CR), with or without complete count recovery or
- occurrence of a proven or probable IFI as defined by EORTC/MSG criteria, or
- 12 weeks have elapsed from the start of therapy, or
- development of unacceptable toxicity, or
- patient's withdrawal from the study (patient or investigator decision), or

#### • patient's death

Isavuconazonium sulfate will be provided at no cost to the patients participating in this study.

#### 6.3 Therapeutic drug monitoring

Isavuconazole plasma concentrations will be determined immediately before dosing on days 8 and 15 using a validated liquid chromatography-mass spectroscopy assay as previously described. These studies will be performed in the laboratory of [name] at the University of Texas Health Sciences Center in San Antonio. 0.5 ml of plasma will be required for the assay. Blood will be collected in EDTA tubes. Plasma will be separated from the blood and frozen. Samples will be shipped in batches on dry ice.

#### 6.4 In vitro susceptibility testing of fungal isolates

This will be performed in the laboratory of Dr. [name] according to the methods of the Clinical and Laboratory Standards Institute for all IFIs that occur during the study for which a specimen is available for fungal culture.

#### 6.5 Long-term follow-up

The Long-Term Follow-Up schedule begins at the end of treatment assessment and continues until death. All patients who receive at least one dose of study drug will be followed for survival every 6-12 months by telephone call to patient, family, local physician, surface or electronic mail. All patient follow up will continue under DR09-0223. A separate informed consent for that study will be required. Patients may be removed from this current protocol and followed up on the DR09-0223 after completing all protocol related assessments.

# 7 PRE-TREATMENT EVALUATION (all procedures must be completed within the week preceding study treatment initiation)

- 7.1 Complete history and physical examination including demographics, concurrent medications, ECOG performance status, vital signs, height and weight.
- 7.2 Informed consent.
- 7.3 Baseline serum or urine pregnancy test.
- 7.4 Baseline complete blood count (CBC) and differential.
- 7.5 Baseline comprehensive metabolic panel (CMP, defined below in study calendar).
- 7.6 Baseline electrocardiogram (ECG).
- 7.7 Baseline chest x-ray (computed tomography (CT) of chest (± sinuses) if patient is febrile and/or presents with signs/symptoms of respiratory infection (lungs or sinus)).
- 7.8 Baseline assessment of bone marrow iron stores (to be done on bone marrow obtained assessment of status of AML/MDS, separate bone marrow examination not required for study). Failure to perform this will not be considered a protocol deviation or violation.

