# 2.9 Warnings and Precautions

#### 2.9.1 Hepatic adverse drug reactions

Hepatic adverse drug reactions (e.g., elevations in alanine aminotransferase (ALT), aspartate aminotransferase (AST), alkaline phosphatase, total bilirubin) have been reported in clinical trials. The elevations in liver-related laboratory tests were generally reversible and did not require discontinuation of isavuconazonium sulfate. Cases of more severe hepatic adverse drug reactions including hepatitis, cholestasis or hepatic failure including death have been reported in patients with serious underlying medical conditions (e.g., hematologic malignancy) during treatment with azole antifungal agents, including isavuconazonium sulfate. Liver function tests should be performed at the start and during the course of isavuconazonium sulfate therapy. Patients who develop abnormal liver-related laboratory tests during isavuconazonium sulfate therapy should be monitored for the development of more severe hepatic injury. Isavuconazonium sulfate should be discontinued if clinical signs and symptoms consistent with liver disease develop that may be attributable to the drug.

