#### STUDY CALENDAR

Vital signs	Х	х			Х			Х			Х			Х
Height	Х													
Weight	Х	Х			Х			Х			Х			Х
Performance status	Х	х			Х			х			Х			Х
CBC w/diff, plts (at least 1-2 times per week during study) g	Х	Х	Х	Х	х	Х	Х	Х	Х	Х	Х	Х	х	Х
CMP a at least weekly	Х	х	Х	Х	Х	х	х	х	Х	Х	Х	Х	х	Х
EKG (baseline and day 10)	Х		Х											
Adverse event evaluation		X											X	Х
Chest x-ray	Х	If any fever	If any sign or symptom of pulmonary infection or neutropenic (ANC < 500/mm  ) fever develops.											
CT scan of chest (±sinuses)	X b	Withi or syn	Within 3 ( $\pm$ 1) days of development of neutropenic (ANC <500/mm  ) fever or any sign or symptom of respiratory infection (lungs or sinus).											
Blood cultures		If patient develops fever (single oral temp $\geq 101^{\circ}$ F (38.3°C) or oral temp $\geq 100.4^{\circ}$ F (38°C) sustained x 1 hour).												
Iron staining of bone marrow	Х	When	Whenever bone marrow is sampled for assessment of disease status of AML/MDS.											
ß-HCG	X d													
Isavuconazole levels e			Х	Х										
Antimicrobial susceptibility testing of fungal isolates	Any time a breakthrough fungal infection occurs and a sample is available for fungal culture.													

 
*Within 1 week prior to study treatment initiation.
 
A: Isavuconazonium sulfate: 372 mg (200 mg of isavuconazole) daily.
 
a: Albumin, alkaline phosphatase, total bilirubin, bicarbonate, BUN, calcium, chloride, creatinine, glucose, LDH, phosphorus, potassium, total protein, SGOT [AST], SGPT [ALT], sodium.
 
b: Only if patient is febrile and/or presents with signs/symptoms of respiratory infection (lungs or sinus).
 
c: ±1 week.
 
														

Serum or urine pregnancy test (women of childbearing potential). d:

e: On days 8 and 15 (before the day's dose).

Off-study evaluation (clinic visit or telephone interview). Differential not required if total WBCs  $\leq$  0.5 x 10^9/L. f:

g:

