# **12 REPORTING REQUIREMENTS**

These guidelines will be followed for the recording and reporting of adverse events and SAEs.

- 1. Baseline events will be recorded in the medical history section of the case report form (CRF) and will include the terminology event name, grade and start date of the event.
  - a. Baseline events are any medical condition, symptom, or clinically significant lab abnormality present before the informed consent form (ICF) is signed.
    - i. Hematologic laboratory abnormalities will not be recorded as baseline events for patients with acute leukemia, myelodysplastic syndrome, chronic lymphocytic leukemia, or chronic myeloid leukemia in blast phase.
    - ii. If exact start date is unknown, month and year or year may be used as the start date of the baseline event.
- 2. The maximum grade of the adverse event will be captured per course of protocol defined visit date.
- 3. These adverse events will be recorded in the case report form:
  - a. Any grade adverse event that is possibly, probably or definitely related to the study drugs(s).
  - b. All serious adverse events regardless of attribution to the study drug(s).
  - c. Any grade adverse event regardless of attribution to the study drug(s) that results in any dose modification.
- 4. Hematologic adverse events will not be recorded or reported for studies in patients with acute leukemia, myelodysplastic syndrome, chronic lymphocytic leukemia, or chronic myeloid leukemia in blast phase except for:
  - a. Prolonged myelosuppression as defined by the NCI-CTCAE criteria specific for leukemia, e.g., marrow hypocellularity on day 42 or later (≥6 weeks) from start of therapy without evidence of leukemia (<5% blasts), or that results in dose modifications, interruptions or meets the protocol definition of DLT or SAE.
- 5. SAEs will be reported according to institutional policy.
- 6. Protocol specific language regarding the recording and reporting of adverse and serious adverse events will be followed in the event of discordance between the protocol and Leukemia Department-specific adverse event recording and reporting guidelines.

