- Unless otherwise noted, the electronic SAE application (eSAE) will be utilized for safety reporting to the IND Office and MDACC IRB.
- SAEs will be captured from the time of the first protocol-specific intervention, until 30 days after the last dose of drug, unless the participant withdraws consent. SAEs must be followed until clinical recovery is complete and laboratory tests have returned to baseline, progression of the event has stabilized, or there has been acceptable resolution of the event.
- Additionally, any SAEs that occur after the 30 day time period that are related to the study treatment must be reported to the IND Office. This may include the development of a secondary malignancy.

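### The adverse event baseline closes at consent rather than first dose, so toxicity from AML/MDS treatment begun in between can look new on isavuconazole

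*Combined protocol and SAP*

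**What the plan says.** Five provisions bear on where the safety baseline lies.

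- **Baseline events.** Section 12, item 1a: "Baseline events are any medical condition, symptom, or clinically significant lab abnormality present before the informed consent form (ICF) is signed". The cut-off is consent, not the first dose.
- **Pre-treatment window.** The title of section 7, which lists consent and the baseline CMP among other items, states: "all procedures must be completed within the week preceding study treatment initiation". The Study Calendar footnote agrees: "Within 1 week prior to study treatment initiation".
- **Lead time of AML/MDS treatment.** Section 5.1.1 admits patients "who have either begun (within 4 days of starting study drug) or are planned to begin specific treatment for their AML/MDS".
- **Start of safety capture.** Section 4.2.2.10 sets the endpoint as "AEs throughout the duration of isavuconazole prophylaxis until 30 days after the last dose of study drug". The SAE part of section 12 says "SAEs will be captured from the time of the first protocol-specific intervention, until 30 days after the last dose of drug", without defining that intervention.
- **Toxicity rule.** Section 11 counts clinically relevant non-hematologic toxicity of grade 3 or higher, prolonged grade 4 hematologic toxicity, or an SAE, with wording on definite, probable or possible relation to study drug. It does not refer to the grade before the first dose.

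On study, section 8.1 repeats history and physical examination at drug initiation, and section 8.3 asks for a CMP at least weekly. Neither assessment is named as the safety baseline, and the Week 1 CMP has no stated timing relative to the first dose.

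**The concern.** The cut-off for baseline events and the start of drug exposure are different days, and chemotherapy may begin between them. A laboratory abnormality or symptom arising in that interval is not a baseline event under section 12. The plan does not require a chemistry sample after AML/MDS treatment has begun and before the first dose, and it does not define an adverse event as new or worsened since that dose. An abnormality that was already present can therefore look as if it began on isavuconazole.

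Liver tests are the clearest case. Section 2.9.1 describes hepatic reactions to the drug and says "Liver function tests should be performed at the start and during the course of isavuconazonium sulfate therapy", but the only chemistry that must precede the first dose may also precede chemotherapy. With no concurrent control arm, the comparison of each patient with his or her own pre-dose state is an important way of separating background toxicity from drug effect. At stake are the adverse event proportions and the count that feeds the toxicity stopping rule.

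**Working it through.** **1. The window.** Consent and the baseline CMP may fall as early as day −7 (section 7, Study Calendar). AML/MDS treatment may begin as early as day −4 (section 5.1.1). With the full lead used, consent and CMP can precede chemotherapy by up to 7 − 4 = 3 days, and up to 4 days of chemotherapy can lie between baseline and first dose.

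**2. Who falls in the gap.**

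| Order of events | Chemotherapy toxicity present before first dose |
|---|---|
| Chemotherapy, then consent and CMP, then first dose | Baseline if present before consent |
| Consent or CMP, then chemotherapy, then first dose | Not a baseline event if it arose after consent; no required laboratory value if it arose after the CMP |
| Consent and CMP, then first dose, then chemotherapy | None exists |

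Only the second row is affected. The documents do not say how many patients that will be.

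**3. Reproducing Tables 3 and 4.** Inputs from section 11: prior beta(0.6, 1.4); stop if Pr(p(tox) > 0.3 | data) > 0.9; looks every 10 patients; maximum 100. With x toxicities in n patients the posterior is beta(0.6 + x, 1.4 + n − x), and the boundary is the smallest x whose tail above 0.3 exceeds 0.9.

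- n = 10: the tail is 0.880 for x = 5 and 0.962 for x = 6, so the boundary is 6.
- n = 20: the tail is 0.807 for x = 8 and 0.906 for x = 9, so the boundary is 9.
- All nine boundaries from 10 to 90 patients match Table 3.

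Exact binomial recursion over those boundaries gives P(stop early) of 0.0002, 0.017, 0.259, 0.858 and 1.000 at true rates of 0.1, 0.2, 0.3, 0.4 and 0.6. Table 4 prints 0.0002, 0.02, 0.26, 0.86 and 1.0.

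**4. Sensitivity.** The documents give no misattribution rate. As an assumption, add 3 or 5 percentage points to the counted toxicity rate and rerun the recursion on the Table 3 boundaries.

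| True rate | P(stop), nothing added | +3 points | +5 points |
|---|---|---|---|
| 0.10 | 0.0002 | 0.001 (at 0.13) | 0.0025 (at 0.15) |
| 0.20 | 0.017 | 0.043 (at 0.23) | 0.077 (at 0.25) |
| 0.30 | 0.26 | 0.44 (at 0.33) | 0.58 (at 0.35) |

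An alternative assumption is that a share m of all patients is misattributed independently of true toxicity p. The counted rate is then 1 − (1 − p)(1 − m). For p = 0.20 and m = 0.05 it is 1 − 0.80 × 0.95 = 0.24, with P(stop) 0.058. For p = 0.30 and m = 0.05 it is 1 − 0.70 × 0.95 = 0.335, with P(stop) 0.48. The direction is the same and the effect somewhat smaller.

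**The case against.** The strongest reply is that the baseline definition does not by itself charge anything to isavuconazole; a causality judgement does. Section 12, item 3 records a non-serious event only if it is at least possibly related or leads to a dose modification, and the toxicity definition in section 11 carries relatedness wording too. An abnormality known to predate the first dose should not be called related to a drug not yet given. This stands, and it means that misattribution is not automatic. It does not close the gap, because the judgement depends on a pre-dose value that the plan does not require, and because possible relation is enough. It is also unclear whether the relatedness wording in section 11 covers all three limbs of the definition or only SAEs.

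Second, section 8.1 requires an examination at drug initiation. That helps with symptoms and signs, but it includes no chemistry, and section 12 still closes the baseline at consent.

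Third, the affected group is limited to the second row of the first table. That also stands.

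A reader might go further and infer any of the following. The documents do not support them.

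- **That all chemotherapy toxicity present at first dose is excluded from baseline.** Toxicity present before consent is baseline, whenever chemotherapy began.
- **That pre-dose SAEs enter the adverse event endpoint.** The window in section 4.2.2.10 starts with prophylaxis, the calendar has no pre-study adverse event evaluation, and the undefined starting point for SAE capture may be the first dose itself.
- **That the stopping rule will be badly distorted.** The added points have no source. The largest shifts shown are at 30%, the rule's own threshold; at a true rate of 10% the effect is negligible.

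**Conclusion.** The point holds as a misplaced cut-off with a limited reach. The baseline for adverse events is tied to consent, and no provision requires chemistry between the start of AML/MDS treatment and the first dose or restricts counting to events new or worsened since that dose. It affects patients consented or sampled before chemotherapy and dosed after it began. Counting against isavuconazole also generally needs a judgement of at least possible relation.

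The size cannot be derived from the documents. The 3 to 5 added points are an assumption, and the resulting stopping probabilities show sensitivity rather than an expected bias. Tables 3 and 4 reproduce and need no correction. This is a cheap improvement worth making before safety data accumulate.

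**What to change.** 1. **Section 12, item 1a.** Define baseline events as those present before the first dose of study drug, with the grade at that time.
2. **Study Calendar.** When AML/MDS treatment has already begun, specify that the scheduled Week 1 CMP is drawn before the first dose. Use the last pre-dose value as the safety baseline.
3. **Section 11 and Analysis Plan.** Count as an adverse event or toxicity only what starts, or worsens in grade, after the first dose. List any SAE captured before the first dose separately.

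The cost is wording in three places and a constraint on the timing of one blood draw that is already scheduled. No test is added and the eligibility criteria do not change. What remains is chemotherapy toxicity that arises or worsens after the first dose: no baseline rule removes it, and it still rests on causality judgement.
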